4.2. Sample Size Justification

The primary objective of the study is estimation of the sensitivity and false positive rate of OTL38 and NIR.

[REDACTED]

4.3. Schedule of assessments

5. ANALYSIS POPULATIONS

The efficacy results will be generated for 3 populations:

Safety Analysis Set (SAS): The safety analysis set will include all patients exposed to OTL38 and/or the imaging system.

Full Analysis Set (FAS): [REDACTED]

- | [REDACTED]
- | [REDACTED]

Per Protocol Analysis Set (PPAS): [REDACTED]

- | [REDACTED]
- | [REDACTED]
- | [REDACTED]
- | [REDACTED]

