5.4 Patient Discontinuation Criteria

Although a single dose of study drug is infused on Day 1, a patient may be withdrawn from the study for any of the following reasons:

- Request of the patient or patient's representative
- AEs or adverse device effects (ADEs) based on the judgment of the Investigator
- The Investigator decides that it is in the patient's best interest
- The patient is noncompliant with the protocol
- Lost to follow-up
- Death

If a subject is withdrawn at any time, the reason(s) will be recorded on the relevant page of the electronic case report form (eCRF).

Patients discontinued due to AEs or ADEs will be monitored until resolution or stability of the event based on the judgment of the investigator.

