5.8.1.1 Visit 1 (Screening, up to Day -28)

Prior to the initiation of study-specific screening assessments the Investigator or designee must provide the patient(s) a complete explanation of the purpose and evaluations (procedures and assessments) of the study. Subsequently, the patient must sign and receive a copy of an Informed Consent Form and authorization of use and disclosure of protected health information (PHI) that was approved by the institutional review board (IRB). Once informed consent has been obtained, the eligibility of the patient will be determined, and Screening Period assessments will be performed.

- Signed informed consent
- Complete medical history
- Physical examination
- Height and weight
- Concomitant medication assessment
- Vital signs (temperature, blood pressure, and pulse rate)
- Serum Pregnancy test (for women of childbearing potential)
- 12-lead ECG
- Clinical laboratory assessments including hematology, chemistries, and urine analysis

5.8.1.2 Visit 2- Day of Surgery (Day 1):

- Updated medical history and physical exam
- Concomitant medications assessment
- Clinical laboratory and vital sign assessments will be performed.
- Urine pregnancy test (for women of childbearing potential)
- 12- Lead ECG will be collected at least 15 minutes prior to infusion, and at least 15 minutes prior to surgery after infusion of OTL38 is completed
- A single dose of OTL38 will be infused IV over 60 minutes and will be completed at least one hour prior to initiation of intraoperative imaging and the time will be recorded
- AEs will be recorded during infusion of OTL38
- During and post-surgery any AEs and ADEs will be recorded.

- [REDACTED]

Day 1 – Surgery

This is a phase 2, multi-center, single dose, open-label, exploratory study in suspected lung cancer patients scheduled to undergo endoscopic or thoracic surgery per CT/PET imaging based on standard of care.

[REDACTED]

- [REDACTED]

- [REDACTED]

[Redacted]

[Redacted]	[Redacted]	[Redacted]
[Redacted]	[Redacted]	[Redacted]
[Redacted]	[Redacted]	[Redacted]
[Redacted]	[Redacted]	[Redacted]

[Redacted]

[Redacted]

[Redacted]

[Redacted]

[Redacted]

[Redacted]

[Redacted]

[Redacted]

[Redacted]

[Redacted]

[Redacted]

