8.2.5 Statistical Analysis

8.2.5.1 Primary Efficacy Endpoints

[figure not shown]
The two co-primary efficacy endpoints are the sensitivity and false positive rate:

- Sensitivity or True Positive Rate (TPR)

[Redacted]

- False positive rate (FPR)

[Redacted]

The sensitivity and false positive rates will be analyzed [REDACTED]

8.2.5.2 *Secondary Efficacy Endpoint*

The secondary efficacy endpoint is the proportion of patients with at efficacy endpoint, [REDACTED]

8.2.5.3 *Safety Evaluations*

Safety will be evaluated using the safety analysis set and will include treatment emergent adverse events (TEAEs), adverse device effects (ADEs), serious adverse events (SAEs), vital signs, physical examinations, clinical laboratory measurements, electrocardiograms, and concomitant medications. For all safety assessments, the baseline value will be the last non-missing value recorded for a particular safety parameter before exposure to study drug. Treatment emergent adverse events are adverse events occurring during or after study drug exposure. Adverse device effects occur during or after exposure to the imaging device and classified as device effects by the Investigator. In general, the analysis of safety will be descriptive. No data will be imputed except for partial dates if required to determine if an adverse event is treatment emergent or a medication concomitant with exposure to study drug.

8.2.5.3.1 *Adverse Events and Adverse Device Effects*

Adverse events occurring after the signing of informed consent but prior to exposure to OTL38 administration will be provided in line listings. Treatment emergent adverse events (TEAEs) will be summarized via the MedDRA system organ class and preferred term using subject incidence rates. Data will be tabulated by severity, physician assessment of the relationship to study drug, serious TEAEs, and TEAEs leading to death or study withdrawal. Further description of TEAEs may be defined by temporal onset to study drug infusion. Additional summaries of TEAEs identified as potential ADEs will also be provided.

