3.2. Endpoints

Primary

Sensitivity or True Positive Rate (TPR) [REDACTED]

False positive rate (FPR) [REDACTED]

Secondary

The secondary efficacy endpoint is proportion of patients with at least one CSE as a result of utilizing OTL-38 and Near Infrared Imaging. [REDACTED]

Exploratory

1. [REDACTED]

Safety

1. Incidence rates of all treatment-emergent AEs (TEAEs), adverse device effects (ADEs), and SAEs, from the time of OTL38 administration through follow-up Visit 4.
2. Laboratory parameters (chemistry and hematology) and vital signs collected at: screening, during day of surgery and 7-day follow-up
3. Electrocardiograms (ECG) and physical examinations will be collected at screening, day of infusion, and within 24 hours prior to discharge.

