7. DEMOGRAPHIC AND BASELINE CHARACTERISTICS

7.1. Subject Disposition

Subject disposition will be presented for all screened subjects, including number of subjects screen failed and number of subjects enrolled (all subjects).

Summary tables for subject disposition will be presented for all subjects.

Number and percentage of subjects in the following categories will be summarized as appropriate:

- Enrolled (All Subjects, number only)
- Safety Analysis Set
- Full Analysis Set
- Per Protocol Analysis Set

For the summary of the following, the percentage will be based on the Safety Analysis Set:

- Surgery Performed
- Imaging Performed
- Completed study
- Prematurely discontinued the study and the reasons for discontinuations

In addition, total duration of the study will be summarized based on the Safety Set by race and by dose cohort.

Two listings will be presented for Subject Disposition and Major Protocol Deviations.

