8.3. Exploratory Analyses

8.4. Subgroup Analysis

9. SAFETY

The safety of all patients enrolled in this study will be recorded from the time of study drug administration and throughout the course of the study that will end with Visit 4 (Day 32).

Safety will be evaluated using the safety analysis set and will include treatment emergent adverse events (TEAEs), adverse device effects (ADEs), serious adverse events (SAEs), vital signs, physical examinations, clinical laboratory measurements, electrocardiograms, and concomitant medications.

For all safety assessments, the baseline value will be the last non-missing value recorded for a particular safety parameter before exposure to study drug. Treatment emergent adverse events are adverse events occurring during or after study drug exposure. Adverse device effects occur during or after exposure to the imaging device and classified as device effects by the Investigator. In general, the analysis of safety will be descriptive. No data will be imputed except for partial dates if required to determine if an adverse event is treatment emergent or a medication concomitant with exposure to study drug.

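### Adverse device effects are evaluated in a drug-and/or-device safety set, so any patient never exposed to the device would dilute their incidence

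*SAP*

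**What the plan says.** Protocol 4.2 and SAP 3.1 make the safety of the imaging systems a secondary objective. SAP 3.2 puts ADEs on an incidence scale: "Incidence rates of all treatment-emergent AEs (TEAEs), adverse device effects (ADEs), and SAEs, from the time of OTL38 administration through follow-up Visit 4".

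SAP 5 defines the population: "The safety analysis set will include all patients exposed to OTL38 and/or the imaging system". Protocol 8.2.2 gives the same definition. Protocol 8.2.5.3 and SAP 9 then assign that set to all safety evaluation and name ADEs in the list. The protocol sentence begins "Safety will be evaluated using the safety analysis set and will include treatment emergent adverse events (TEAEs), adverse device effects (ADEs" and continues through the other safety measures.

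The same two sections say when an ADE can arise. In the protocol: "Adverse device effects occur during or after exposure to the imaging device and classified as device effects by the Investigator". In SAP 9: "Adverse device effects occur during or after exposure to the imaging device".

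Three further places bear on whether a safety-set patient could be without device exposure:

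- Protocol 5.8.1.2 says the infusion "will be completed at least one hour prior to initiation of intraoperative imaging".
- Protocol 5.4 notes that only one dose is given and still says "a patient may be withdrawn from the study for any of the following reasons".
- SAP 7.1 introduces rows for surgery performed and imaging performed with "For the summary of the following, the percentage will be based on the Safety Analysis Set".

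**The concern.** An incidence should be taken over the patients who could have had the event. By the plan's own wording, only a patient exposed to the imaging device can have an ADE, yet the set assigned to ADEs also admits patients exposed to OTL38 alone. Each such patient adds one to the denominator and nothing to the numerator. The error runs in one direction only: it makes the device look safer. It falls on the measure that answers the secondary device-safety objective.

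Such patients are possible under the plan. There is at least an hour between the end of infusion and the start of imaging, withdrawal after dosing is allowed, and the disposition table provides for fewer than all safety-set patients being imaged. How many there will be is not stated.

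**Working it through.** The plan states no ADE rate, no expected number of unexposed patients and no readable denominator rule for ADEs, so it has no figure of its own to reproduce.

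**Inputs**

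- N, the safety-set size: 110 for illustration. This is the enrolment maximum in the protocol synopsis; the actual safety-set size is not given.
- k, safety-set patients with no device exposure: not in the documents. Assumed 0, 1, 3 and 10.
- x, patients with an ADE: not in the documents. Assumed 0, 1 and 5.

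**Formulas**

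- Incidence on the full safety set: x / N.
- Incidence on device-exposed patients: x / (N − k).
- Relative understatement for x ≥ 1: [x/(N − k) − x/N] ÷ [x/(N − k)] = 1 − (N − k)/N = k/N.
- Absolute shortfall: x/(N − k) − x/N = xk / [N(N − k)].

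The relative understatement does not depend on x once x is at least 1. An exact-fraction check confirmed the k/N identity for every N from 2 to 110, every k from 1 to N − 1 and every x from 1 to N − k.

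**Results with N = 110**

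| k | Exposed patients | Rate, x = 5 | Shift from full set, x = 5 (percentage points) | Relative understatement k/N | Rate, x = 1 |
|---|---|---|---|---|---|
| 0 | 110 | 5/110 = 4.55% | 0 | 0% | 1/110 = 0.91% |
| 1 | 109 | 5/109 = 4.59% | 0.04 | 0.9% | 1/109 = 0.92% |
| 3 | 107 | 5/107 = 4.67% | 0.13 | 2.7% | 1/107 = 0.93% |
| 10 | 100 | 5/100 = 5.00% | 0.45 | 9.1% | 1/100 = 1.00% |

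With x = 0 the rate is 0% at every k. Only the upper confidence limit moves: the one-sided 95% bound 1 − 0.05^(1/n) is 2.69% at n = 110 and 2.98% at n = 99 (k = 11).

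**Scale.** The exact (Clopper–Pearson) 95% interval is 1.5% to 10.3% for 5/110 and 1.6% to 11.3% for 5/100. The largest shift in the table, 0.45 percentage points, is small beside either interval.

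**What counts as exposed.** The number of patients not imaged is only an upper bound on k. The ADE definition in protocol 7.2.1 reaches events arising from deployment of the device, so a patient for whom the system was set up but never used for imaging may count as exposed. Protocol 5.8.5 records fluorescence start and stop times only for in situ imaging, so those times alone would miss such a patient.

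**The case against.** The strongest reply is that the denominator is inferred. Naming a population in which safety is evaluated is not the same as a rule for ADE percentages. The authors do write such a rule elsewhere: protocol 8.2.5.5 states the denominator for concomitant-medication percentages. Parts of the SAP are also redacted, including a block after section 9.5. The presentation conventions are section 10 in the contents list but 11 in the body, so a section may be hidden. All of this stands as a caution, and the full safety set is therefore the natural reading and not a stated table rule. However, the set definition and the sentence assigning it to ADEs are readable in both documents. The SAP's presentation conventions also require every summary table to show the analysis-set sample size, which favours the full-set reading.

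The second reply is that the matter is minor. Nothing shows that k exceeds zero, and a broad definition of exposure makes it smaller. Safety is descriptive, and no readable decision rule uses ADE incidence. A common denominator also keeps the ADE tables comparable with the tables of treatment-emergent events. These points limit the importance of the concern without answering it, because the bias has a known direction and can be removed before k is known.

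The third reply is that a reader could rebuild the rate from the imaging-performed count in SAP 7.1 and the per-patient camera listing in SAP 7.6. This is approximately true, but set-up without imaging could be misclassified.

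**Conclusion.** The concern holds, as a low-severity point. On the readable text, ADEs are evaluated in a set that can include patients who could not have had one. Where that happens and at least one ADE occurs, the reported incidence is too low by k/N relative to the incidence in device-exposed patients; k/N is not a difference in percentage points. With an assumed 5 ADE patients and N = 110, the shift is 0.04 to 0.45 percentage points for k from 1 to 10. If every safety-set patient is exposed to the device, or if no ADE occurs, the point estimate does not change.

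The conclusion rests on reading the safety set as the ADE denominator and on no redacted text saying otherwise. The values of k and x are assumptions, and N is the enrolment ceiling. Efficacy results and the overall safety set are unaffected.

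**What to change.** Keep the safety set for overall safety. State in protocol 8.2.2 and in SAP 5 and 9 that ADE incidence uses the safety-set patients exposed to the imaging system, with exposure including deployment or set-up in the operating room, so that it matches the definition in protocol 7.2.1. Show that N beside the safety-set N in the ADE tables. Do not derive exposure from fluorescence times alone. If redacted text already sets this denominator, it is enough to confirm it.

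The cost is a sentence in each place and one denominator flag in the analysis data. If set-up without imaging is not already recorded, one yes/no eCRF item may be needed. The downside is that the work has no effect if k proves to be zero, and that ADE percentages may become slightly less favourable if it does not.

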6. GENERAL ASPECTS OF THE STATISTICAL ANALYSIS

The following general rules will be followed for the analysis specified in this SAP. In addition, [Section 10](#) further detailed analysis presentation conventions.

Continuous data will be summarized using the following descriptive summary statistics: the number of observations (n), mean, SD, median, minimum value (min), and maximum value (max).

Categorical data will be summarized using counts and percentages.

Baseline value will be defined as the most recent non-missing scheduled measurement before the administration of the first dose of study drug.

Change from baseline value will be calculated as postbaseline value minus baseline value.

Unscheduled visits: Patient data obtained during unscheduled visits/assessments will not be summarized but will be included in patient data listings only; except for the analysis of maximum values and maximum changes from baseline.

Incomplete and/or missing data will not be imputed. [REDACTED]

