8.2.5.3.2 Clinical Laboratory Evaluations

The analysis of laboratory parameters will include descriptive statistics for the change from baseline to each post-baseline study visit as well as shifts from baseline to each post-baseline study visit for categorical lab parameters. In addition, shift tables (i.e., low-normal-high at baseline versus low-normal-high at last visit) will be provided where appropriate. Urinalysis and pregnancy results will not be summarized but will be provided in a data listing. For all relevant laboratory data, values above or below normal limits will be flagged along with the direction of abnormality in line listings.

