9.2. Clinical Laboratory Assessments

Summary statistics will be presented for each laboratory parameter by visit for hematology, biochemistry, and urinalysis, for both actual values and changes from Baseline.

Shift tables of laboratory data from baseline to post-baseline value, will be presented based on the upper and/or lower limits of normal.

All laboratory data will be listed and values outside of normal ranges will be flagged.

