9.4. Vital Signs

Vital signs (including the assessments of systolic and diastolic blood pressure, heart rate, respiration rate, and body temperature), and their change from baseline will be summarized each scheduled visit.

All data, including unscheduled visits will be listed.

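### The SAP admits unscheduled laboratory and vital-sign values only to a maximum-value analysis that its laboratory and vital-sign sections do not specify, so these values enter no laboratory or vital-sign summary table

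*SAP*

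**What the plan says.** SAP 6 sets the general rule for unscheduled visits and assessments: "Patient data obtained during unscheduled visits/assessments will not be summarized but will be included in patient data listings only". One exception follows: "except for the analysis of maximum values and maximum changes from baseline".

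The sections that would carry that exception read as follows.

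- **SAP 9.2, by-visit statistics:** "Summary statistics will be presented for each laboratory parameter by visit for hematology, biochemistry, and urinalysis, for both actual values and changes from Baseline".
- **SAP 9.2, shift tables:** "Shift tables of laboratory data from baseline to post-baseline value, will be presented based on the upper and/or lower limits of normal". The text does not say whether the post-baseline value is the last, the worst or the one at each visit.
- **SAP 9.2, listing:** "All laboratory data will be listed and values outside of normal ranges will be flagged".
- **SAP 9.4, vital signs:** the values "and their change from baseline will be summarized each scheduled visit". All data, unscheduled visits included, are listed.

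Protocol 8.2.5.3.2 plans shifts from baseline to each post-baseline visit for categorical laboratory parameters. It then adds, where appropriate, a shift table of "low-normal-high at baseline versus low-normal-high at last visit". Protocol 8.2.5.3.3 summarises vital signs in a similar way.

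The scheduled time points in SAP 3.2 are few: "Laboratory parameters (chemistry and hematology) and vital signs collected at: screening, during day of surgery and 7-day follow-up".

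**The concern.** Safety and tolerability of a single dose is a primary objective. Scheduled sampling after the dose is sparse, and unscheduled assessments are often made because something is clinically wrong. They are therefore among the values most likely to be abnormal. A rule that keeps them out of the summaries tilts the laboratory and vital-sign tables towards showing no effect.

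SAP 6 appears to recognise this by reserving a place for unscheduled values in an extreme-value analysis. If that analysis is not specified, the exception does nothing. A last-visit shift does not help, because an abnormality that has resolved by the last visit is counted as normal.

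ECG and physical examination results are listed only (SAP 9.3 and 9.5). The laboratory and vital-sign tables are thus the main planned summaries of objective safety measurements.

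**Working it through.** The plan gives no figure to reproduce. The check follows one value through the planned outputs: an abnormal result from an unscheduled assessment after infusion and before the Day 7 visit.

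**Window.** The protocol synopsis sets the visit at Day 7 ± 4, so it falls between Day 7 − 4 = 3 and Day 7 + 4 = 11. The visible text does not say whether the day-of-surgery laboratory sample comes before or after infusion. If it comes before, the Day 7 visit gives the only scheduled post-dose laboratory value. That is an assumption, since no schedule of assessments is visible in either document.

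**Where the value goes.**

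1. By-visit laboratory statistics (SAP 9.2): excluded by the SAP 6 rule.
2. By-visit vital-sign statistics (SAP 9.4): excluded, because they are tied to scheduled visits.
3. Laboratory shift tables (SAP 9.2): excluded by the SAP 6 rule, whichever post-baseline value is meant.
4. Protocol shifts (8.2.5.3.2): the by-visit shifts are tied to study visits, and the additional table uses the last visit. Neither is a worst-value shift.
5. Maximum values and maximum changes: allowed by SAP 6, but not specified in SAP 9.2 or 9.4, nor in protocol 8.2.5.3.2 or 8.2.5.3.3.
6. Listings: included. Out-of-range laboratory values are flagged.
7. Adverse event tables (SAP 9.1): included as an event, whatever the visit, if reported as one. Protocol 7.3.2 requires this for clinically significant laboratory abnormalities, either within a clinical syndrome or, if isolated, as an event in their own right.

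Routes 1 to 5 are closed on the visible text. Routes 6 and 7 are open.

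**What route 7 does not carry.** It depends on the investigator's judgement of clinical significance. Where a syndrome is reported, protocol 7.3.2 does not require the laboratory abnormality to be recorded separately, so its direction and size are not tabulated. Section 7.3.2 concerns laboratory values only. The visible text has no matching rule for vital signs, which reach a table only if the investigator reports an adverse event.

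**Direction.** Even if performed, an analysis limited to maxima would miss falls, such as low counts or low blood pressure.

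**Illustration only.** Unscheduled cases missing from a shift table = patients × incidence of transient abnormality × share caught on an unscheduled draw. With the protocol's upper limit of 110 patients, an assumed incidence of 3% to 10% and an assumed share of 25% to 75%, the range runs from 110 × 0.03 × 0.25 = 0.8 to 110 × 0.10 × 0.75 = 8.25, or about 1 to 8. Neither rate comes from the documents, and some of these cases would appear as adverse events.

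**The case against.** A reader might infer that abnormal values from for-cause draws appear in no safety table at all. The documents do not support that. A patient unwell after exposure has an adverse event to be recorded under protocol 7.3.1. Clinically significant laboratory abnormalities are captured under 7.3.2, and SAP 9.1 tabulates treatment-emergent events without restriction to scheduled visits. Many for-cause draws will belong to events already counted. This part of the objection stands, and it limits the point to laboratory and vital-sign tables.

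A reader might also infer that the protocol's only shift is to the last visit. It is not: by-visit shifts come first and the last-visit table is additional. SAP 9.2 does not mention the last visit at all.

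Nor can one say that the maximum-value analysis is absent from the whole SAP. A redacted block follows SAP 9.5 and could contain one. SAP 9.2 and 9.4, however, show no redaction and point to no other section.

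Finally, summarising scheduled data by visit and listing the rest is a coherent descriptive approach, and a single-arm study cannot separate drug effects from surgical ones in a worst-value table. Both statements are fair. They support keeping the by-visit tables as they are. They do not explain an exception in SAP 6 that refers to an unspecified analysis.

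**Conclusion.** The point holds for laboratory and vital-sign summaries. On the visible text, an unscheduled abnormal value between infusion and the Day 7 (±4) visit enters none of these tables. It is tabulated only if it becomes a treatment-emergent adverse event, and otherwise stays in listings. What the tables lose is the numeric value itself, laboratory abnormalities not judged clinically significant, and vital-sign changes not reported as events.

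The size cannot be stated, because the documents give neither the frequency of transient abnormalities nor the frequency of unscheduled assessments. The range of about 1 to 8 cases shows only what assumed rates would imply for one table, and should not be read as the size of the problem.

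The conclusion assumes that the redacted text does not specify the missing analysis. The change is worth making because it concerns a primary objective and costs little. Adverse event reporting and the listings mitigate the gap without closing it.

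**What to change.** - **SAP 9.2:** define the shift table as baseline to worst post-baseline value, with lowest and highest shown separately, and state that unscheduled assessments are included.
- **SAP 9.2 and 9.4:** add summaries of minimum and maximum post-baseline values and of the corresponding changes from baseline, including unscheduled data. Extend the exception in SAP 6 to cover minima and the worst-value shift. If the analysis already exists in redacted text, a cross-reference to it, checked for low-direction values, is enough for this part.
- **By-visit tables:** keep them on scheduled data.
- **Protocol 8.2.5.3.2:** align the last-visit shift with the SAP definition.
- **Baseline:** SAP 6 restricts it to scheduled measurements, while SAP 9 takes the last non-missing value recorded before exposure. Settle this in the same edit, since the new changes and shifts depend on it.

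The cost is SAP wording and one or two descriptive tables from data already collected and listed. The tables will look less favourable and will include surgery-related abnormalities that this single-arm design cannot separate from drug effect. A footnote should say so.
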